6.2 Dose modifications

6.2.1 Dose modifications and dose delay

For patients who do not tolerate the protocol-specified dosing schedule, dose adjustments are permitted in order to allow the patient to continue the study treatment. All dose modifications should be based on the worst preceding toxicity (**Table 6**). Dosage changes must be recorded on the Dosage Administration Record CRF.

The following guidelines should be applied.

Each patient will be allowed 3 dose reductions. Patients should discontinue Infigratinib if toxicities persist following 3 dose reductions (**Table 5**).

Following resolution of toxicity to baseline or \leq Grade 1, treatment is resumed at either the same or lower dose of study drug as per the criteria in **Table 6**. If treatment is resumed at the same dose of study drug, and the same toxicity recurs with the same or worse severity regardless of duration, dose must be reduced to the next lower dose level. If treatment is resumed at the lower dose of study drug, and the same toxicity recurs with the same or worse severity, the patient should have a second dose reduction.

Patients who discontinue the study for a study related adverse event or an abnormal laboratory value must be followed as described in Section 8.

In exceptional situations, study treatment may continue even if the patient experienced one of the treatment stopping rules. The decision to allow for continuation of treatment will be made on a case-by-case basis following discussion with the Principal Investigator (Sponsor).

Situations that may allow for continuation of treatment include the following:

- A dose delay of > 14 days has occurred, but the patient is clearly benefiting from study treatment (i.e., stable disease, partial response, or complete response) and it is the investigator's opinion that no safety concerns are present. If the patient is clearly benefiting from the study treatment (i.e. stable disease, partial response, or complete response), and in the opinion of the investigator no safety concerns are present, after discussion with QED Therapeutics Medical Monitor, the patient may remain on the study treatment.
- A third or subsequent reduction (to 50 mg) in dose may be allowed if the patient is clearly benefiting from study treatment (i.e., stable disease, partial response, or complete response) but is experiencing adverse events that prevent continued treatment at the already reduced dose.

Table 5: Dose reduction table

Dose reduction				

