Grade 3: QTcF $>$ 500msec as identified on the ECG by the investigator	
 • Hold Infigratinib. • Monitor patient with hourly ECGs until the QTcF has returned to baseline. • Perform further monitoring as clinically indicated. • Exclude other causes of QTcF prolongation such as hypokalemia, hypomagnesaemia and decreased blood oxygenation. • Patients should receive appropriate electrolyte replacement and should not receive further Infigratinib until electrolytes are documented to be within normal limits. 
Once the QTcF prolongation has resolved and if the QTcF prolongation was confirmed by the central reader, patients may be re-treated at one lower dose level at the investigator's discretion
 
 • ECG assessments should be performed for 2 additional cycles at the same frequency as in cycle 1 or as clinically indicated 
 ◦ If ECG assessments show no QTcF \geq 481 msec, for subsequent cycles ECG monitoring will be performed as per visit schedule. ◦ If ECG assessments are still abnormal (QTcF \geq 481 msec and \leq 500 msec), then ECG monitoring must continue at the same frequency as in cycle 1 or as clinically indicated, for all subsequent cycles • Patients who experience recurrent QTcF \geq 500msec after one dose reduction will be discontinued from study. 
NB: If ventricular arrhythmia or Torsades de Pointes is observed in a patient, he/she will be discontinued from the study.
 
Whenever QTcF $>$ 500msec is observed, a plasma sample for determination of Infigratinib concentration

Worst Toxicity CTCAE v5.0 Grade (unless otherwise specified)	Recommended Dose Modifications any time during a cycle of therapy
	should be obtained with the time of sample collection noted.
Cardiac disorders - others Grade \geq 3, or congestive heart failure \geq 2	Discontinue patient from study treatment.
Investigations-Hematology	
ANC decreased (Neutropenia) Grade 3 (ANC $< 1.0 - 0.5 \times 10^9/L$)	Hold dose of Infigratinib until resolved to CTCAE Grade \leq 1 or baseline, then: 
 • If resolved within \leq 7 days, maintain dose level of Infigratinib • If resolved within $>$ 7 days, \downarrow 1 dose level of Infigratinib. Grade 4 (ANC $< 0.5 \times 10^9/L$)

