7.1.4 Discontinuation of study treatment

Patients may voluntarily discontinue from the study treatment for any reason at any time. If a patient decides to discontinue from the study treatment, the investigator should make a reasonable effort (e.g. telephone, e-mail, letter) to understand the primary reason for this decision and record this information in the patient's chart and on the appropriate CRF pages. They may be considered withdrawn if they state an intention to withdraw, fail to return for visits, or become lost to follow-up for any other reason.

Study treatment must be discontinued under the following circumstances:

- Adverse events, that results in a significant risk to the patient's safety.
- The following deviation from the prescribed dose regimen for study treatment: dose interruption of > 14 days from the intended day of the next scheduled dose, unless otherwise specified in Section 6.1.3
- Pregnancy
- Any other protocol deviation that results in a significant risk to the patient's safety
- Patients who discontinue study treatment should NOT be considered withdrawn from the study. They should return for the assessments indicated in **Table 7** (end of study treatment visit) and then enter the follow-up epoch. If they fail to return for these assessments for unknown reasons, every effort (e.g. telephone, email, letter) should be made to contact them (Lost to follow-up).

For patients who discontinue treatment for reasons other than documented disease progression, death, lost to follow-up, or withdrawal of consent, tumor assessments must continue to be performed every 8 weeks until documented disease progression, death, lost to follow-up, or withdrawal of consent.

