7.2 Assessment types

7.2.1 Efficacy assessment

Tumor response will be evaluated locally by the investigator according to the guideline (see Appendix 3) based on the Response Evaluation Criteria in Solid Tumors (RECIST) Version 1.1 (Eisenhauer et al 2009). Each patient will be evaluated for all potential sites of tumor lesions at screening/baseline and every 8 weeks after starting study treatment until disease progression.

CT (Computed Tomography) /MRI (Magnetic Resonance Imaging) scans will be performed at baseline within 28 days before start of treatment and subsequently every 8 weeks from treatment start until progression of disease.

After baseline, the first assessment should be performed at Cycle 3 Day 1 (+7 day window) and all subsequent assessments should be performed within ± 7 days of the scheduled day of assessment. The same method of assessment and the same technique should be used to characterize each individual and reported lesion at baseline and during follow-up. If a patient discontinues treatment for reasons other than radiological documentation of progression of disease, an efficacy assessment should be performed at the time of End of Treatment unless a CT/MRI for tumor measurement was performed ≤ 4 weeks earlier.

Chest, abdomen, and pelvis CT scans are required for all patients at baseline. If at baseline, a patient is known to have a contraindication to CT i.v. contrast media or develops a contraindication during the trial, a contrast-enhanced MRI (if possible) of chest, abdomen, and pelvis should be performed.

For the patients with skeletal lesions suspected at baseline, a whole-body bone scan (e.g. TC 99, NaF PET, etc.) should be performed. Skeletal lesions which are identified on a whole body bone scan at baseline, which are not visible on the chest, abdomen or pelvis CT/MRI scan, should be re-imaged at baseline with localized CT, MRI or x-ray, and followed at scheduled visits (every 8 weeks).

Partial Response (PR) and Complete Response (CR) should be confirmed by repeat assessments performed at least 4 weeks and no later than 6 weeks after the criteria for response are first met.

PET/CT may be used only if it is of similar diagnostic quality as a CT performed without PET, including the utilization of oral and intravenous contrast media. While FDG-PET may complement CT scans in assessing progression per RECIST 1.1 (Appendix 3) FDG-PET assessments should be disregarded for this protocol.

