7.2.2.7 Cardiac assessments

ECG evaluations will be conducted centrally. For all patients prior to the first administration of Infigratinib, a minimum of 3 sequential 12-lead ECGs, separated by at least 5-10 minutes, must be performed on Day 1 of Cycle 1. This is necessary to get an accurate baseline QTcF calculation. 12-lead ECGs are to be performed at the following time-points:

- At screening and/or baseline
- Cycle 1 Day 1: pre-dose and 2-hr post-dose, \pm 15 min. (3 sequential)
- Cycle 1 Day 15: pre-dose (3 sequential)
- All Subsequent cycles, day 1: pre-dose (3 sequential)
- At the end of treatment

Clinically significant abnormalities present when the patient signed informed consent should be reported on the Medical History eCRF page. Clinically significant findings must be discussed with the The Ohio State University Principal Investigator (Sponsor) prior to enrolling the patient in the study. New or worsened clinically significant findings occurring after informed consent must be recorded on the AE eCRF page.

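### Table 6 prints the hemoglobin Grade 3 threshold in the wrong unit, gives two instructions at a QTcF of exactly 500 msec after a dose reduction, and is silent on restart when the central reader does not confirm a QTcF hold

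*Combined protocol and SAP*

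**What the plan says.** All three items are in Table 6 of the combined protocol and SAP, section 6.2.1.

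- **Hemoglobin, Grade 3.** Drug is held until recovery and then continued at the same dose. The threshold is printed as below 8.0 mg/dL, with a note that transfusion is indicated. Exclusion criterion 15c (section 5.3) sets its hemoglobin limit at 9.0 g/dL.
- **QTcF, after re-treatment at a lower dose.** One bullet covers values from 481 to 500 msec, both ends included, and calls for continued ECG monitoring. A later bullet takes a patient off study for a recurrent QTcF of 500 msec or more after one dose reduction. The original hold applies above "500msec as identified on the ECG by the investigator".
- **QTcF, restart after the hold.** Once the prolongation has resolved, "if the QTcF prolongation was confirmed by the central reader, patients may be re-treated at one lower dose level", at the investigator's discretion. Drug is also withheld until electrolytes are documented as normal. Section 7.2.2.7 adds that "ECG evaluations will be conducted centrally". The general rule in section 6.2.1 is that "treatment is resumed at either the same or lower dose of study drug as per the criteria in" Table 6.

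**The concern.** Sites at several institutions act directly on this table, so each threshold should give one answer.

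Read as a number, the hemoglobin threshold would never trigger a hold in practice. At exactly 500 msec after a reduction, one bullet asks for more ECGs and another ends participation. In the restart rule, the hold depends on the local reading and the release depends on the central one, but only one of the two possible central results is followed by an instruction. Taken literally, a patient whose QTcF was truly prolonged has a printed way back to treatment, while a patient whose ECG was over-read locally has none.

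What is at stake is consistent patient management across sites, not the analysis of response.

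**Working it through.** **Hemoglobin.** Inputs: 8.0 mg/dL (Table 6) and 9.0 g/dL (exclusion 15c).

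- Conversion: 8.0 / 1000 = 0.008 g/dL.
- Against the entry limit: 9.0 / 0.008 = 1125, so the printed threshold is 1125 times lower than the limit for joining the study.
- Illustration: 7.5 g/dL is 7500 mg/dL. This is not below 8.0 mg/dL, so the printed number does not trigger the hold. It is below 8.0 g/dL, so the corrected number does.

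**QTcF boundary.** The printed inequalities, evaluated at integer values:

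| QTcF (msec) | Monitoring band, 481 to 500 inclusive | Hold, above 500 | Stop after one reduction, 500 or more |
|---|---|---|---|
| 480 | no | no | no |
| 481 | yes | no | no |
| 499 | yes | no | no |
| 500 | **yes** | no | **yes** |
| 501 | no | yes | yes |

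The monitoring band and the stop overlap at one integer, 500. The overlap arises only for a recurrence after a dose reduction. For a first event there is no conflict: 500 means maintain dose and above 500 means hold. The stop (500 or more) also uses a different inequality from the hold (above 500), although it describes a recurrence of the event that caused the hold.

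Either repair empties the overlap. With monitoring from 481 to below 500 and the stop at 500 or more, 500 is a stop only. With monitoring from 481 to 500 and the stop above 500, 500 is monitoring only and the stop matches the hold.

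**Restart.** No arithmetic applies. The possible outcomes are:

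| Central reading of a locally read QTcF above 500 msec | Printed restart instruction |
|---|---|
| Confirmed | One dose level lower after resolution, at the investigator's discretion |
| Not confirmed | None |

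The general resumption rule does not fill the empty cell, because it refers the choice of dose back to Table 6. Other rows do print a same-dose path, for example Grade 3 neutropenia, thrombocytopenia without bleeding, and AST or ALT elevation when resolved within 7 days. The QTcF Grade 3 row does not.

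**The case against.** The best counter-argument is that a competent site would get all three right. The hemoglobin row is keyed to CTCAE grade and mentions transfusion, so the unit is a visible misprint. At 500 msec, the monitoring bullet sets ECG frequency and does not order continued dosing; the later bullet is specific to recurrence and would naturally govern. On restart, the column gives recommendations, the sentence is permissive, and it can be read as saying that central confirmation is what justifies the reduction. The adjacent Grade 1 and 2 row already maintains dose at 481 to 500 msec. Exposure is also small: section 1.2.1.4.1 reports no effect on ECG intervals, and QTcF above 470 msec is an exclusion.

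Most of this stands, and it is why the severity is low and the restart item is a clarification rather than an error. It does not make the printed unit right or supply the missing precedence at 500 msec.

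A reader might infer something stronger: that an unconfirmed reading pushes the patient into the section 7.1.4 stop for a "dose interruption of > 14 days from the intended day of the next scheduled dose", and that in Cycles 1 and 2 this always happens before a scan could support the listed exception in section 6.2.1 ("A dose delay of > 14 days has occurred, but the patient is clearly benefiting from study treatment (i.e., stable disease, partial response"). The documents do not support that chain.

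- It needs a site to keep withholding drug for over 14 days after QTcF has returned to baseline and the central reader has found no event. Nothing suggests this would happen.
- The timing claim is not general. The Grade 1 and 2 row repeats the Cycle 1 ECG frequency for two more cycles, and Cycle 1 includes a Day 15 ECG ("Cycle 1 Day 15: pre-dose (3 sequential"). A patient with earlier mild prolongation can therefore have an ECG on Cycle 2 Day 15, which is Day 28 + 15 = 43. The limit is first exceeded 15 days after the intended dose, on Day 43 + 15 = 58. The first scan is at Cycle 3 Day 1 ("After baseline, the first assessment should be performed at Cycle 3 Day 1 (+7 day window"), nominally Day 2 × 28 + 1 = 57, which comes first.
- Section 7.1 allows assessments as clinically indicated, and the exceptions listed in section 6.2.1 are introduced as examples.

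**Conclusion.** The point holds at low severity. The hemoglobin unit is wrong as printed, by a factor of 1000. The QTcF rules overlap at one integer value, 500 msec, and only after one dose reduction. The restart gap is real on the text but is mainly an omission that sites would probably fill sensibly.

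The documents give no frequency for readings the central reader does not confirm, so none is assumed. It is assumed that 8.0 g/dL is the intended threshold, from the unit in exclusion 15c and the reference to transfusion. No loss of treatment under the 14-day rule is claimed, and there is no effect on the response-rate design, sample size or error rates.

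**What to change.** Amend Table 6 as follows.

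1. **Hemoglobin Grade 3:** change mg/dL to g/dL.
2. **QTcF of exactly 500 msec after one reduction:** either state that the stop takes precedence and end the monitoring band below 500 (the more cautious option), or change the stop to above 500 so that it matches the hold. This is a clinical choice for the sponsor.
3. **QTcF Grade 3 restart:** add a sentence such as: *If the central reader does not confirm QTcF >500 msec, then once QTcF has returned to baseline and electrolytes are documented within normal limits, treatment may resume at the same dose at the investigator's discretion, with ECG monitoring per the Grade 1-2 row if the central value is 481-500 msec and the patient is asymptomatic; the one-level reduction applies to confirmed events.*

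The electrolyte condition should apply whatever the central value, because the row already imposes it on every held patient.

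The cost is one unit, one inequality or precedence note, and one sentence, all of which can go into the next amendment. No visits, data collection or analyses change.

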Worst Toxicity CTCAE v5.0 Grade (unless otherwise specified)	Recommended Dose Modifications any time during a cycle of therapy
Laboratory / Metabolic disorders	
Asymptomatic amylase and/or lipase elevation	
Grade 3 (> 2.0 - 5.0 x ULN with signs or symptoms; >5.0 x ULN and asymptomatic)
 
 • Hold dose of Infigratinib until resolved to CTCAE Grade \leq 2. • ↓ 1 dose level of Infigratinib 
For recurrent Grade 3 asymptomatic lipase or amylase elevation despite dose reduction, drug should be held and continuation of therapy should be discussed with the medical monitor following resolution to \leq Grade 2.

Grade 4 (>5.0 x ULN and with signs and symptoms)	
For any Grade 4 asymptomatic lipase or amylase elevation, drug should be held and continuation of therapy should be discussed with the medical monitor following resolution to \leq Grade 2.

	
Note: A CT scan or other imaging study to assess the pancreas, liver, and gallbladder should be performed as clinically indicated within 1 week of the first occurrence of any CTCAE \geq Grade 3 amylase and/or lipase.

Hyperphosphatemia	
Grade 1: Laboratory finding only and intervention not indicated	
Maintain dose level of Infigratinib and optimize phosphate lowering therapy as clinically indicated.

Grade 2: Noninvasive intervention indicated	
Maintain dose level of Infigratinib and optimize phosphate lowering therapy as clinically indicated.

Grade 3: Severe or medically significant but not immediately life-threatening; hospitalization or prolongation of existing hospitalization indicated	
Hold Infigratinib until resolved \leq Grade 2. Restart at same dose level with maximal phosphate binder dosing.

Grade 4: Life-threatening consequences; urgent intervention indicated (e.g. dialysis)	
Hold Infigratinib until resolved \leq Grade 2. Reduce one dose level dose level with maximal phosphate binder dosing.

	
It is recommended that phosphate binder dosing continues during Infigratinib dose interruptions for hyperphosphatemia and that serum phosphorus values be monitored frequently, e.g. every 2-3 days.

	
Phosphate binder dosing should be held during the week off Infigratinib therapy each cycle (Days 22-28) and during Infigratinib dose interruptions for non-hyperphosphatemia adverse events.

Worst Toxicity CTCAE v5.0 Grade (unless otherwise specified)	Recommended Dose Modifications any time during a cycle of therapy

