Hypercalcemia Serum calcium Grade 2 or 3	Hold Infigratinib dose until resolved to Grade 1 or baseline: 
 if resolved within \leq 7 days after suspending Infigratinib, maintain dose level if resolved within $>$ 7 days after suspending Infigratinib, \downarrow 1 dose level
Serum calcium \geq Grade 4	Discontinue patient from the study
Nervous system disorders	
Neurotoxicity Grade 2	Omit dose of Infigratinib until resolved to CTCAE Grade \leq 1, then \downarrow 1 dose level of Infigratinib
Grade \geq 3	Discontinue patient from study drug treatment
GI disorders	
Pancreatitis Grade 2 (Enzyme elevation; radiologic findings only)	Hold Infigratinib dose until resolved to Grade 1 or baseline: 
 if resolved within \leq 7 days after suspending Infigratinib, maintain dose level if resolved within $>$ 7 days after suspending Infigratinib, \downarrow 1 dose level
Grade \geq 3 (Severe pain; vomiting; medical intervention indicated)	Discontinue patient from study drug treatment
Diarrhea Grade 1	Maintain dose level of Infigratinib, initiate anti-diarrheal treatment
Grade 2	
 Hold dose of Infigratinib until resolved to CTCAE Grade \leq 1 Optimize anti-diarrheal treatment, maintain dose level of Infigratinib. For reoccurrence of diarrhea CTCAE Grade 2, hold dose of Infigratinib until resolved to CTCAE Grade \leq 1, \downarrow Infigratinib by 1 dose level

Worst Toxicity CTCAE v5.0 Grade (unless otherwise specified)	Recommended Dose Modifications any time during a cycle of therapy
Grade 3	
 • Hold dose of Infigratinib until resolved to CTCAE Grade \leq 1 • Optimize anti-diarrheal treatment • \downarrow Infigratinib by 1 dose level • For reoccurrence of diarrhea CTCAE Grade 3, despite optimal antidiarrheal treatment, discontinue patient from study treatment.
Grade 4	
Discontinue patient from study treatment.
 
Note: Antidiarrheal medication is recommended at the first sign of abdominal cramping, loose stools or overt diarrhea

Vomiting Grade 2 not controlled by optimal anti-emetic therapy Grade 3 not controlled by optimal anti-emetic therapy or Grade 4	Hold Infigratinib doses until \leq Grade 1, \downarrow 1 dose level Discontinue patient from study
Eye Disorders (confirmed by ophthalmologic examination)	

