Retinal disorders Grade 2 central serous retinopathy and central serous retinopathy -like events Grade 3 central serous retinopathy and central serous retinopathy-like events and any other Grade 3 eye disorders \geq Grade 1 retinal vein occlusion, Grade 4 central serous retinopathy and central serous retinopathy-like events, and Grade 4 other eye disorders	Hold Infigratinib until resolved to \leq Grade 1 and continue ophthalmologic evaluation 
 • If resolved within \leq 14 days, \downarrow Infigratinib by 1 dose level • If resolved within $>$ 14 days, discontinue Infigratinib Hold Infigratinib until resolved to Grade \leq 1. 
 • If resolved within \leq 14 days, \downarrow Infigratinib by 1 dose level • If resolved within $>$ 14 days, discontinue Infigratinib Discontinue Infigratinib
Other ocular/visual toxicity \geq Grade 3	Hold Infigratinib until resolution to \leq Grade 1 If resolution within \leq 14 days, \downarrow 1 dose level, otherwise discontinue Infigratinib
General disorders	

Worst Toxicity CTCAE v5.0 Grade (unless otherwise specified)	Recommended Dose Modifications any time during a cycle of therapy
Fatigue Grade 3	Hold dose of Infigratinib until resolved to CTCAE Grade ≤ 1. If resolved within ≤ 7 days, maintain dose level of Infigratinib.
Other clinically significant AEs	
Grade 3	Hold dose of Infigratinib until resolved to CTCAE Grade ≤ 1, then ↓ 1 dose level of Infigratinib.
Grade 4	Discontinue patient from study treatment.
All dose modifications should be based on the worst preceding toxicity. Once a dose reduction has occurred dose re-escalation may be allowed on a case by case basis after discussion with the Principal Investigator/Sponsor. Patients who require more than two dose reductions of Infigratinib will be generally discontinued from study drug treatment.	

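### Table 6's Grade 4 amylase/lipase instruction is worded for a case its own definitions rule out, so the action for a symptomatic elevation above 5 x ULN is unclear

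*Combined protocol and SAP*

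**What the plan says.** Table 6 grades toxicity by "Worst Toxicity CTCAE v5.0 Grade (unless otherwise specified", and the amylase/lipase row prints its own grade definitions. The relevant entries are:

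- **Row heading:** "Asymptomatic amylase and/or lipase elevation".
- **Grade 3 definition:** "Grade 3 (> 2.0 - 5.0 x ULN with signs or symptoms; >5.0 x ULN and asymptomatic". The action is to hold until Grade 2 or lower, then reduce one dose level. A further rule covers recurrent Grade 3 elevations after a reduction, but only asymptomatic ones.
- **Grade 4 definition:** "Grade 4 (>5.0 x ULN and with signs and symptoms".
- **Grade 4 action:** "For any Grade 4 asymptomatic lipase or amylase elevation, drug should be held and continuation of therapy should be discussed with the medical monitor", once the event has resolved to Grade 2 or lower.

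Two other rows of Table 6 can bear on the same patient. The Pancreatitis row, at Grade 3 or higher ("Severe pain; vomiting; medical intervention indicated"), ends study drug. The catch-all row, "Other clinically significant AEs", says at Grade 4: "Discontinue patient from study treatment".

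The closing note to the table bases modifications on the worst preceding toxicity. It does not say which row governs when more than one could cover an event.

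**The concern.** A dose-modification table has to lead every site from the same event to the same action. Here the heading and the action sentence limit the row to asymptomatic patients, while the Grade 4 definition admits only symptomatic ones. The Grade 4 instruction cannot be applied as worded, and the event that really is Grade 4 under this row is left to interpretation.

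Two things are at stake. One is a safety table that does not say clearly what happens after a symptomatic Grade 4 enzyme elevation. The other is the tolerability data: Table 3 lists dose interruptions, reductions and dose intensity as endpoints, Section 7.2.2 counts adverse events leading to delay or discontinuation, and Section 10.5 tabulates events resulting in discontinuation. In a multi-site trial these counts should not depend on how a site reads one line.

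**Working it through.** No sample-size or power figure is involved. The check sets each combination of enzyme level and symptom status against the row's definitions and actions. I read the Grade 4 phrase on signs and symptoms simply as symptomatic.

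**Step 1: grade each state by the row's definitions.**

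| Enzyme level | Symptoms | Grade under this row | Action written in this row |
|---|---|---|---|
| >2.0 to 5.0 x ULN | no | below 3 | none |
| >2.0 to 5.0 x ULN | yes | 3 (first limb) | the Grade 3 action, but outside the heading; recurrence not covered |
| >5.0 x ULN | no | 3 (second limb) | the Grade 3 action and the recurrence rule |
| >5.0 x ULN | yes | 4 | an action worded only for asymptomatic cases |

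**Step 2: look for a state that is both Grade 4 and asymptomatic.** There is none. An asymptomatic elevation stays at Grade 3 however high it goes, so the condition in the Grade 4 action describes an empty set.

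**Step 3: trace the state that is Grade 4.** For a symptomatic elevation above 5.0 x ULN:

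- If the grade label governs, the action is to hold and, after resolution to Grade 2 or lower, discuss continuation with the medical monitor.
- If the word *asymptomatic* governs, this row has no action and the event falls to the catch-all Grade 4 line, which is to discontinue.
- If the patient also meets the Pancreatitis criteria at Grade 3 or higher, that row adds its own instruction to discontinue. It is silent otherwise.

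**Step 4: check Grade 3 for the same mismatch.** The first limb of the definition is symptomatic, so it lies outside the heading. The recurrence rule names only asymptomatic Grade 3, so a recurrent symptomatic Grade 3 elevation has no recurrence instruction in this row.

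**Step 5: bound the frequency.** Section 1.2.1.4.1 reports Grade 3 or 4 lipase increase in 7.9% of subjects in the earlier cholangiocarcinoma study. Applied to the 50 planned patients, 0.079 x 50 = 3.95, or about 4. That figure pools Grades 3 and 4 and gives no symptom status. If the rate carries over, the expected number of symptomatic Grade 4 lipase events lies between 0 and about 4. The documents allow nothing narrower.

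**The case against.** The strongest reply is that the practical reach is small. On either reading of Grade 4, drug stops immediately. The alternative to discontinuation is not free continuation, because a restart requires resolution to Grade 2 or lower and a discussion with the medical monitor, which is a central check on divergence between sites. The table's imaging note applies from Grade 3 upwards on both readings. Section 7.1.4 separately requires discontinuation for adverse events that put the patient at significant risk. Section 6.2.1 also lets treatment continue case by case after a stopping rule is met, so even the discontinue branch is not absolute. All of this stands, and it limits the consequence to whether a later restart is open by default.

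A reader might also infer more than the documents support:

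- **That several rows fire together and contradict each other.** They do not. If the Grade 4 label governs, the event has its own row and is not an *other* event. If *asymptomatic* governs, the catch-all fills a gap. It is one ambiguous line, and the Pancreatitis row enters only when its own criteria are met.
- **That about 4 patients will be affected.** That figure includes asymptomatic elevations above 5.0 x ULN, which are Grade 3 and have a clear written action.
- **That the response rate is affected.** Nothing in the documents demonstrates this.

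The reply does not remove the mismatch. The worst-preceding-toxicity note ranks severity without choosing a row, and the case-by-case exception presupposes knowing whether a stopping rule was met.

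**Conclusion.** The row is wrong as written. Its Grade 4 action rests on a condition that its own definitions exclude, and no other section resolves this. A symptomatic elevation above 5.0 x ULN can lead to a hold with a possible restart at one site and to discontinuation at another. Both sites could point to the table in support.

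The effect is confined to dose-interruption and discontinuation summaries and to clarity of patient management. Its frequency is not given; about 4 of 50 is a ceiling on the expected lipase count, and only if the earlier study's rate applies here. Sample size, power and type I error do not depend on it. This is an internal inconsistency that should be corrected. It does not call the design into question.

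**What to change.** The clinical team should reconcile the row's heading, its Grade 3 and Grade 4 definitions, and its action and recurrence wording, so that each instruction states the enzyme level and symptom status it covers. The table should also say which row governs when an elevation meets the Pancreatitis or catch-all row as well. Which clinical action is right is for that team, and none is proposed here.

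The cost is a wording change to one row of Table 6, plus a sentence on precedence, in the next amendment. It needs no new data collection and no change to the analysis.
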